2.5 Blinding

This is a double-blind study using open-label investigational product. Pharmacy staff will be unblinded for investigational product preparation. Investigators, study team members and study participants will be blinded to the dose level given (4 mg, 8 mg, or placebo) and will remain blinded throughout the study.

3 DATA ANALYSIS CONSIDERATION

Output processing will be undertaken by [REDACTED], using SAS Version 9.3 (or higher). All Tables, Listings and Figures (TLFs) will be produced in landscape format. In general, all data will be listed by the participant and visit. The number of variables presented in each listing can vary. Please refer to mock tables, listings and figures.

No formal statistical analysis will be conducted for this study. Summary statistics appropriate for categorical and continuous variables will be presented by treatment group and all inferences will be based on clinical evaluation of those results.

Data will be summarized by treatment group where appropriate. The total number of participants (N) in each treatment group under the stated population will be displayed in the header of summary tables.

Continuous data will be summarized using descriptive statistics for continuous variables. Unless otherwise stated, descriptive statistics will include the number of participants (n), mean, standard deviation (SD), minimum, median and maximum. When n=0, summary statistics (other than n) will be displayed as blank fields. When n=1, only the minimum and maximum will be reported; all other summary statistics will be displayed as blank entries. The number of missing values associated with an n that is less than the expected n for the visit or time point of interest will also be presented.

For summary tables of categorical variables, counts and percentages will be presented. The count [n] indicates the actual number of participants with a particular value of a variable or event, which should always be less than or equal to the total number of participants in the respective treatment group [N]. The number and percentage of participants with missing values for a variable/category/event will also be presented for the resulting visits/time points under the “Missing” category.

Percentage will be obtained by: $\% = (n/N) * 100$.

All dates will be displayed in DDMMYY format.

Decimal Precision Convention:

The minimum and maximum statistics will be presented to the same number of decimal places as the original data. The mean and median will be presented to one more decimal place than the original data, whereas the standard deviation will be presented to two more decimal places than the original data. Unless otherwise stated, all percentages will be expressed to one decimal place.

Handling of Missing Data: Imputation of missing data will not be performed and will be analyzed as missing. To handle missing or partial AEs and concomitant medication dates, the following rules will be applied.

For partial Start Dates:

1. If the year is unknown, then do not impute the date but assign a missing value.
2. If the month is unknown, then:
 - i. If the year matches the year of the first dose date, then impute the month and day of the dose date.
 - ii. Otherwise, assign “January.”
3. If the day is unknown, then:
 - i. If the month and year match the month and year of the first dose date, then impute the day of the dose date.
 - ii. Otherwise, assign “01.”

For partial end dates:

1. If the year is unknown, then do not impute the date but assign a missing value.
2. If the month is unknown, then assign “December.”
3. If the day is unknown, then assign the last day of the month.

After implementing the rules above, to determine whether AEs (or medications) with missing start or stop dates are pre-treatment or on/after treatment, the following strategy will be used:

1. If the start date and stop date are both missing, then the most conservative approach is taken and the AE (or medication) is considered to be treatment emergent (or concomitant medication).

2. If the start date is missing but the stop date is not missing and is on or after the date of signed informed consent, then the most conservative approach is taken, and the AE (or medication) is considered to be treatment emergent (or concomitant medication).
3. If the start date is missing but the stop date is not missing and is before the date of signed informed consent, then the AE (or medication) is considered to be before treatment (or prior medication).
4. If the start date is not missing but the stop date is missing, then the most conservative approach is taken, and medication is considered to be concomitant while the AE is defined by start date.
5. If the Adverse Event Relationship flag is missing, the relationship for adverse event will be imputed and will be considered as Definitely related. If the Adverse Event Severity flag is missing, the severity will be imputed and will be considered as severe & undesirable (Grade 3).

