2.2 Study Design

This is a Phase 2a, double-blind, placebo-controlled, multi-center study to assess the efficacy and safety of a repeat-dose regimen of IRL201104 in participants with active EoE. Eligible participants will undergo an up-to-6-week screening period to stabilize current therapy, confirm diagnosis by histologic assessment, and other eligibility criteria. Participant compliance to DSQ reporting will be assessed for at least 2 consecutive weeks prior to randomization. At the end of the screening period, eligible participants will be randomized in a 1:1:1 ratio to one of 3 arms, as displayed in Figure 1

- Arm 1: IRL201104 4 mg IV with endoscopy and esophageal biopsy 2 weeks after last dose (Week 4).
- Arm 2: IRL201104 8 mg IV with endoscopy and esophageal biopsy 2 weeks after last dose (Week 4).
- Arm 3: Placebo IV with endoscopy and esophageal biopsy 2 weeks after last dose (Week 4).

Participants will receive IRL201104 (4 mg or 8 mg IV) or placebo on Days 0, 7, and 14 (3 total doses over 14 days). Participants will be evaluated for clinical and histologic responses at Week 4. All participants will be assessed for safety and continued biomarker sampling through Week 8.

Figure 1: Overview on the Study Procedures

D = day; EGD = esophagogastroduodenoscopy; EOS = End of Study; ICF = informed consent form; IV = intravenous; R = randomization; WK = week

Table 1: Study Schema

The Schedule of Events for the study is

Procedures	Screening Period	Prior to Rand	Rand/ Baseline	Treatment Period				End of Study/ Final Safety	Notes
Visit	V -1	V0	V1	V2	V3	V4	V5	V6	
Week	-6	-	0	1	2	4	6	8	
Day	-	-	0	7	14	28	42	56	
Window	≤ 6 weeks	-	-	± 3 days	± 3 days	± 3 days	± 3 days	± 3 days	
Screening/ Baseline									
Informed consent	X	-	-	-	-	-	-	-	
Demographics/ Medical history review	X	-	-	-	-	-	-	-	
Inclusion/exclusion criteria review	X	X	X	-	-	-	-	-	
Treatment									
Randomization IWRS	-	-	X	-	-	-	-	-	
Administer study treatment	-	-	DBL	DBL	DBL	-	-	-	Pharmacy site staff will be unblinded to prepare the treatment. Investigators, study staff members, and study participants will be blinded to the treatment and dose level (4 mg or 8 mg or placebo) and will remain blinded throughout the study.
Efficacy									
DSQ training and issue handset	X	X	-	-	-	-	-	-	Daily completion of the DSQ starts on the first day it is issued to the participant.

Procedures	Screening Period	Prior to Rand	Rand/ Baseline	Treatment Period				End of Study/ Final Safety	Notes

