7.8 Safety Analysis

The analysis of safety endpoint variables will include assessments of AEs, vital signs, 12-lead ECGs, physical examinations, and clinical laboratory tests. All Safety assessments will be summarized and tabulated as appropriate and will be listed by participant as applicable. All safety analyses will be performed on Safety Analysis Set. No formal statistical analysis will be performed on safety outcomes.

Example: The following variables will be evaluated to assess the safety:

- Adverse Events
- Clinical Laboratory Data
- 12 Lead Electrocardiogram (12-Lead ECG)
- Vital Sign measurements
- Physical Examination

Adverse Events:

Adverse Events will be coded using (MedDRA version 24.0 or latest) AE coding system for purpose of summary tables. Adverse events will be summarized using frequency count and percentage by MedDRA SOC and PT.

“Treatment-emergent” will be defined as starting or worsening after the first dose of investigational product. If the start date is missing, the event is assumed to be treatment emergent.

All AEs and TEAEs during the study will be summarized for the respective treatment group. A participant experiencing the same AEs and TEAEs multiple times will be counted only once for that PT. Similarly, if a participant experience multiple AEs and TEAEs (preferred terms) within the same SOC then that participant will be counted only once for that SOC. When summarizing by severity or relationship, only event with highest severity / relationship will be counted. Adverse events will be dichotomized into related (definitely, probably, and possibly) and unrelated (unlikely and not related) All AEs will be listed in chronological order of the events occurred.

An overview of AE summary will be presented. It will include the following:

- AEs
- Serious AEs
- TEAEs
- Serious TEAEs
- Treatment related TEAEs
- Treatment related Serious TEAEs
- TEAEs leading to study discontinuation
- TEAEs leading to death

The incidence and frequency of AEs will be summarized by treatment according to SOC and PT.

Treatment-Emergent Adverse Events (TEAEs)

A summary of the frequency (number and percentage of participants) of TEAEs will be presented by SOC, PT.

TEAEs will be summarized by treatment, system organ class, preferred term, and severity (mild, moderate, severe and undesirable, life-threatening or disabling and death).

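### For adverse events with a missing or partial start date, the SAP's date rules can count an event as treatment-emergent although its recorded stop date is before the first dose

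*SAP*

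**What the plan says.** SAP section 3 works in two stages.

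**Stage one completes partial dates.** For a start with only the day unknown: "If the month and year match the month and year of the first dose date, then impute the day of the dose date". If the month is also unknown and the year matches the year of first dose, the month and day of first dose are used. If the year itself is unknown: "If the year is unknown, then do not impute the date but assign a missing value". Partial end dates are moved to the latest date they could be.

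**Stage two classifies what is still missing.** Its stated aim is "to determine whether AEs (or medications) with missing start or stop dates are pre-treatment or on/after treatment".
- Rule 1: both dates missing, treatment-emergent.
- Rule 2 makes an event treatment-emergent under this condition: "If the start date is missing but the stop date is not missing and is on or after the date of signed informed consent".
- Rule 3 makes it pre-treatment under this one: "If the start date is missing but the stop date is not missing and is before the date of signed informed consent".

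The same sentences cover adverse events and medications.

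SAP 7.8 gives the definition in two sentences. Treatment-emergent "will be defined as starting or worsening after the first dose of investigational product". Then: "If the start date is missing, the event is assumed to be treatment emergent". Protocol 15.3.3 contains both sentences as well.

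On the interval between consent and dosing, SAP 2.2 says: "Eligible participants will undergo an up-to-6-week screening period". Protocol 12.6.3 collects adverse events from the signing of consent, so events in that interval are in the database.

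**The concern.** The boundary between pre-treatment and on-treatment is the first dose. An event with a recorded end before that dose cannot have begun or worsened after it, whatever is unknown about its start. The section 3 rules do not use this information. Stage one never compares an imputed start with the stop. Rules 2 and 3 compare the stop with consent, which is the boundary SAP 7.4 uses for prior versus concomitant medication.

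The consequence would be a false count in the treatment-emergent tables, and under stage one also a record with its start after its stop. Screening includes an endoscopy with 19 biopsies (protocol Table 5: 9 + 4 esophageal, 6 gastric and duodenal), so events in that period are plausible. Section 3 also sets a missing relationship to definitely related, so a misplaced event could move into the treatment-related table too. SAP section 3 rests all inference on clinical reading of descriptive tables by arm, and the arms are small.

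**Working it through.** The plan states no figure to reproduce. The check is to run the rules on constructed dates and compare the results with the two sentences of SAP 7.8.

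**Inputs**
- First dose = day 0.
- Consent = day −42. This is an assumption at the maximum: 6 weeks × 7 = 42 days (SAP 2.2).
- Planned size 36, randomized 1:1:1 (SAP 2.4): 36 / 3 = 12 per arm.

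**(a) Partial start date.** Take an illustrative first dose on 20 March.
- Start recorded as March with the day unknown; stop recorded as 10 March. Month and year match, so the start is imputed as 20 March, which is 20 − 10 = 10 days after the event ended.
- Start recorded as the year only; stop recorded as 10 March. The year matches, so the start is again imputed as 20 March, with the same result.

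After imputation neither date is missing, so rules 1 to 4 do not apply and the event is classified by its imputed start. It becomes treatment-emergent if the program counts a start on the dosing day as after first dose. With no recorded day or time of onset, the data cannot settle that.

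The reach of this rule is limited. With a month-and-year match, the stop lies between the first of the dosing month and the day before dosing, so at most 31 − 1 = 30 days before dosing. With a year-only match it can reach back to consent (up to 42 days) if dosing and screening fall in the same calendar year.

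**(b) Start wholly missing.** After stage one, this means the year is unknown.

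| Recorded stop | SAP section 3 | Can sentence 1 of 7.8 be true? | Sentence 2 of 7.8 | First-dose cut-off |
|---|---|---|---|---|
| Missing | Emergent (rule 1) | Yes | Emergent | Emergent |
| Day −50 | Pre-treatment (rule 3) | No | Emergent | Not emergent |
| Day −42, −20 or −1 | Emergent (rule 2) | No | Emergent | Not emergent |
| Day 0 or 10 | Emergent (rule 2) | Yes | Emergent | Emergent |

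The third row is the error: rule 2 gives a classification that sentence 1 cannot support. The second row shows a separate inconsistency: rule 3 departs from sentence 2. Moving the cut-off to first dose changes only the third row.

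**Size.** One participant wrongly counted, with no other treatment-emergent event:
- in an arm of 12: 1 / 12 = 8.3 percentage points;
- over all 36: 1 / 36 = 2.8 points;
- if replacements brought the dosed total to 50 (an assumption, since the planned figure of up to 50 concerns enrollment): 50 / 3 = 16.7 per arm, and 1 / 16.7 = 6.0 points.

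**The case against.** The strongest reply is that rule 2 follows the definition as fully written. The second sentence of SAP 7.8, repeated in protocol 15.3.3, treats any missing start as treatment-emergent and sets no condition on the stop. A reader might infer that rule 2 flatly contradicts the SAP's own definition. The documents do not support that: it conflicts with the first sentence and agrees with the second. This part of the objection stands. It does not save the text, because rule 3 contradicts the second sentence, so sections 3 and 7.8 cannot both be followed as they are. It also says nothing in favour of (a), where the start is imputed and not missing.

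A reader might also infer that every event resolving in screening becomes treatment-emergent. It does not: an event with a complete start date is classified by that date. Case (b) needs an unknown onset year alongside a known stop date, in a study of up to 14 weeks per participant with onset date and time recorded (protocol 12.6.3). That is close to hypothetical. Case (a), where only the day is unknown, is more realistic but should still be uncommon.

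A third tempting inference is that screening procedure events would be attributed to study drug, or that the comparison between arms is biased. Treatment-emergent status is about timing; relatedness is a separate investigator judgement with its own table. All adverse events, including those that are not treatment-emergent, are listed, so a case can be found on review. The trial is randomized and blinded, and nothing in the rules favours one arm.

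Finally, the SAP presents the rule as conservative, and the error is indeed an over-count. That is a fair principle when timing is unknown, but here the recorded stop date settles it. An extra event on placebo would also narrow an apparent difference, so over-counting is not always the cautious direction.

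**Conclusion.** The point holds as a minor defect. For adverse events with a partial or missing start date, section 3 can count as treatment-emergent an event whose recorded stop precedes the first dose. It does so by two routes: imputing the first-dose date with no check against the stop, and using consent as the cut-off when the start is wholly missing. The first is the more likely to occur. Sections 3 and 7.8 also disagree with each other through rule 3.

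Frequency cannot be estimated from the documents and is probably low. The error runs towards over-counting. The 8.3 points per case is an upper figure: it assumes 12 dosed participants in the arm and a participant with no other treatment-emergent event. Route (a) also assumes that the program counts a dosing-day start as after first dose; if it does not, the impossible order of dates remains but the false count does not arise. The documents do not show a systematic misclassification of screening events or a bias between arms.

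**What to change.** Four edits to the SAP:

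1. In section 3, rules 2 and 3, for adverse events only, compare the stop date with the first-dose date. A stop before first dose means not treatment-emergent.
2. In the partial-start rules, cap any imputed start at the recorded stop date. In the March example the start becomes 10 March and the event is pre-treatment.
3. In section 7.8, limit the second sentence to events whose start date is missing and whose stop date is not before the first dose. Without this edit, the change to rules 2 and 3 would leave section 7.8 saying the opposite.
4. Keep consent as the cut-off for medications, in line with SAP 7.4, and separate the adverse-event wording from the medication wording so that each has its own boundary.

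SAP section 1 gives the SAP precedence over the protocol on statistical analysis, so protocol 15.3.3 need not be amended; a line in SAP section 11 recording the departure is enough. The cost is a few lines of text and the matching program conditions. No new data are needed.

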4 DEFINITIONS AND DERIVATIONS

Baseline: Baseline is defined as the last non-missing value (whether from scheduled or unscheduled visit) prior to the first study drug administration.

Change from Baseline: The change from baseline values at all post-baseline visits will be calculated by subtracting the baseline value from the corresponding post-baseline value.

Change from Baseline = Post baseline value - Baseline value.

Percent reduction: The percent reduction is the ratio of the reduction in the post-baseline value to its baseline value multiplied by 100.

$$\text{Percent reduction} = \frac{\text{Post Baseline value} - \text{Baseline value}}{\text{Baseline value}} \times 100$$

End of the Study: The end of the study is defined as the final follow-up visit by the last participant. If the study is terminated prematurely, the study ends when the sponsor notifies the investigator in writing that the study has finished, or when the last participant attends the final follow-up visit, whichever is later.

Study Day: This is the number of days from the date of the first study drug administration to a target date:

$$\begin{aligned} \text{Study Day} &= (\text{Target Date} - \text{Date of the first study drug administration}) + 1 \\ &\quad (\text{If target date is greater than or equal to the date of the first study drug administration}) \\ &\quad \text{or} \\ \text{Study Day} &= (\text{Target Date} - \text{Date of the first study drug administration}) \\ &\quad (\text{If target date is less than date of the first study drug administration.}) \end{aligned}$$

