5.2 Secondary Endpoints

- Absolute change in DSQ score from baseline (see DSQ score definition in Section 7.7.2)
- Proportion of participants achieving peak esophageal intraepithelial eosinophil count of < 15 eos/hpf (Week 4)
- Percent reduction in peak esophageal intraepithelial eosinophil count (eos/hpf) (Week 4)
- The safety endpoints are Monitoring of AEs, physical examinations, vital signs, electrocardiograms (ECGs), clinical laboratory tests, and clinical evaluations. Participants will be asked to monitor all AEs experienced from the time of informed consent until their last study visit.

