7.7 Efficacy Analysis

7.7.1 Analysis of Primary Endpoint

The primary efficacy endpoint is change from baseline in peak esophageal intraepithelial eosinophil count at Week 4.

The change from baseline will be summarized as the n, mean, standard deviation, median, minimum, and maximum by the treatment group of interest using the FAS. Analysis will also be done using the SAS.

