For each DSQ calculation, the sum of the specified question(s) from each reported daily diary with non-missing data over the interval being reported will be obtained, dividing this by the number of reported daily diaries with non-missing data in that same interval. This result will then be multiplied by the interval. This normalizes each DSQ sum over the interval. For the DSQ score, if a response of “No” is recorded for Question 2, the DSQ score will be set to zero for that day. The DSQ calculations during the interval being reported prior to the baseline visit will be defined as the baseline DSQ evaluation. For each 14-day period, at least 8 reported diaries are needed to effectuate a DSQ calculation for that period. If at least 8 diaries are not available, the DSQ result for that 14-day period will be set to missing.

The absolute change in DSQ score from baseline will be summarized as the n, mean, standard deviation, median, minimum, and maximum by treatment group.

Additionally, exploratory endpoint analysis of absolute days without dysphagia will be summarized as the n, mean, standard deviation, median, minimum, and maximum by treatment group. Absolute days without dysphagia will be obtained through a counting process of the number of DSQ records between baseline and Week 8 that the participant reports DSQ question #2 as “No.”

Esophageal intraepithelial Eosinophil

The proportion of participants achieving peak esophageal intraepithelial eosinophil count of < 15 eos/hpf (Week 4) will be summarized using frequency and percentage.

Also, percent reduction in peak esophageal intraepithelial eosinophil count (eos/hpf) (Week 4) will be summarized as the n, mean, standard deviation, median, minimum, and maximum by treatment group.

Also, exploratory endpoint analysis will be performed for esophageal intraepithelial eosinophil. The proportion of participants achieving peak esophageal intraepithelial eosinophil count of ≤ 1 and ≤ 6 eos/hpf (400 \times) at Week 4 will be summarized separately using frequency and percentage.

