11 CHANGES TO ANALYSES SPECIFIED IN PROTOCOL

The below mentioned endpoints will not be analysed for this study.

Eosinophilic Esophagitis Diagnostic Panel (EDP) Transcriptome

RNA sequencing and EDP transcriptome will be evaluated. A molecular EDP has been identified that is composed of 94 EoE genes and distinguishes EoE from control individuals without esophagitis or with GERD ([Wen 2013](#)).

The EDP signature will be evaluated in biopsy samples. Using a method reported by ([Wen 2015](#)), the EoE transcriptome will be determined using the EDP from extracted RNA.

The Relative change will be provided for EDP transcriptome signature by treatment group.

Relative change = $\{(Post\ baseline\ value - Baseline\ value) / Baseline\ value\} * 100$.

Immune Cells and Markers of Inflammation

Immune cells and markers of inflammation include: immune cell phenotyping (T-subsets, B-subsets, and macrophage subsets); A20; serum cytokines; serum IgE/IgG4; and serum eosinophil derived neurotoxin (EDN) for eosinophil activation.

Relative change in immune cells and markers of inflammation pre- and post dose administration at baseline, and Weeks 1, 2, 4, 6, and 8 will be provided. Separate listing will be provided.

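### SAP Section 4 defines percent reduction one way in words and the opposite way in its formula, so the sign of a secondary efficacy endpoint is contradictory

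*SAP*

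**What the plan says.** SAP Section 4 defines percent reduction twice. In words: "The percent reduction is the ratio of the reduction in the post-baseline value to its baseline value multiplied by 100". The displayed equation directly below puts post-baseline minus baseline in the numerator and baseline in the denominator, and multiplies by 100.

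That numerator is the one the same section uses for change from baseline, written in plain text as "Post baseline value - Baseline value". The whole expression appears again in SAP Section 11, where it is labelled relative change.

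SAP Section 5.2 lists the quantity as a secondary endpoint, and Section 7.7.2 says how it is reported, separately for each arm: "percent reduction in peak esophageal intraepithelial eosinophil count (eos/hpf) (Week 4) will be summarized as the n, mean, standard deviation, median, minimum, and maximum". The protocol names the endpoint in Section 6.4.2 but gives no formula. SAP Section 3 says of the output: "Please refer to mock tables, listings and figures". Those mock tables are not among the documents available.

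**The concern.** A reduction is conventionally positive when the value falls, and the SAP's sentence says the same. The formula gives the opposite sign for every participant whose count changes. No text says which of the two governs, or that a negative percent reduction means improvement. The rule in SAP Section 1 that the SAP overrides the protocol cannot settle a conflict inside the SAP.

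What is at stake is the reading of one secondary efficacy table. The study plans no formal tests, and SAP Section 3 rests all inference on clinical evaluation of the summaries, so readers will take the printed signs and extremes at face value. Read literally, a mean percent reduction of -60 says that counts rose. The minimum and maximum, both required, also exchange meaning: under the formula the largest percent reduction belongs to the participant who did worst.

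**Working it through.** **Inputs**

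- Sentence in SAP Section 4: reduction over baseline, times 100. As a formula: S = (baseline - post) / baseline x 100.
- Equation in SAP Section 4: F = (post - baseline) / baseline x 100.
- Protocol Section 8.1, inclusion criterion 9: a screening peak of at least 15 eos/hpf in at least two of three esophageal regions. Baseline is therefore above zero in eligible participants and both ratios are defined.
- The documents give no figure for this endpoint to reproduce. The counts below are assumed for illustration and are not trial data.

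**Step 1: general relation.** S = -F for every participant. Both depend only on the ratio of post to baseline:

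| Post / baseline | F (equation) | S (sentence) |
|---|---|---|
| 0 (full clearance) | -100 | +100 |
| 0.25 | -75 | +75 |
| 0.5 | -50 | +50 |
| 1 (no change) | 0 | 0 |
| 1.5 | +50 | -50 |
| 2 (doubling) | +100 | -100 |

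**Step 2: three assumed participants**

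| Baseline to Week 4 (eos/hpf) | F | S | Absolute change |
|---|---|---|---|
| 60 to 24 | (24 - 60)/60 x 100 = -60 | +60 | -36 |
| 40 to 60 | (60 - 40)/40 x 100 = +50 | -50 | +20 |
| 60 to 0 | (0 - 60)/60 x 100 = -100 | +100 | -60 |

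The percent summaries that the SAP would print:

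| Statistic | F | S |
|---|---|---|
| Mean | -110/3 = -36.7 | +36.7 |
| Median | -60 | +60 |
| SD | 77.67 | 77.67 |
| Minimum | -100 (the participant who cleared) | -50 (the participant who worsened) |
| Maximum | +50 (the participant who worsened) | +100 (the participant who cleared) |

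The mean absolute change is -76/3 = -25.3 under either rule.

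**Step 3: can the range reveal which rule was used?** Not always. Take five assumed participants with baseline 60 and Week 4 counts of 0, 15, 30, 60 and 120. F gives mean -25.0 and median -50.0, S gives +25.0 and +50.0, and the SD is 79.06 for both. Both rules print minimum -100 and maximum +100, but these values belong to opposite participants.

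**Step 4: could the equation be an extraction error?** This is unlikely. Its numerator order matches the plain-text change-from-baseline definition in the same section, and the full expression recurs in Section 11.

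**Step 5: what else uses the formula?** The primary endpoint does not: "The primary efficacy endpoint is change from baseline in peak esophageal intraepithelial eosinophil count at Week 4", an absolute difference. The endpoints defined by thresholds (<15, ≤6 and ≤1 eos/hpf) use the Week 4 count itself. No test or decision rule depends on the sign.

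**The case against.** The strongest reply is that a programmer has only one explicit formula, that it matches the SAP's general change-from-baseline convention, and that the sentence above it is merely loose. The protocol synopsis also uses the word reduction loosely: it describes the primary endpoint as a mean change, with reduction in brackets, although the SAP computes that endpoint as post minus baseline. On this view there are not two rival rules, only a mislabelled percent change. Under the formula the percent and absolute summaries would point the same way, and readers of the primary table already meet negative values as improvement and the maximum as the worst participant. In addition, the relative-change formula in Section 11 belongs to analyses that have been dropped, the matching -100 and +100 range is a constructed case, and a mock table may carry a clarifying footnote.

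Much of this stands. The formula is the more likely rule to be coded, the Section 11 expression is evidence about labelling and not a competing live definition, and the consequence is limited. The contradiction remains, however. If the formula governs, the endpoint's name and its definition in words are wrong; if the sentence governs, the formula is wrong. A footnote in an unseen table shell could reduce the risk of misreading, but it would not correct Section 4.

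**Conclusion.** The concern holds. As written, SAP Section 4 gives a sentence and a formula that differ in sign for every non-zero value of a named secondary efficacy endpoint. If the formula is followed, a table of percent reduction shows -100 for full clearance and +100 for a doubling. These two values are exact at any baseline above zero; the means, medians and SDs in the illustrations depend on the assumed counts.

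The effect is confined to sign, labelling, and the meaning of minimum and maximum. Magnitudes and SDs are unchanged, and a careful reader could detect the problem by comparing the absolute change in the same counts. It should still be fixed, because the endpoint is interpreted directly from its printed summaries. How the table would finally be labelled cannot be judged without the mock tables.

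**What to change.** Choose one of two corrections in SAP Section 4:

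1. Change the formula to (baseline - post-baseline) / baseline x 100, and state that a positive value means a fall in the count. This keeps the protocol's endpoint name. The percent summary then has the opposite sign to the absolute change in the same counts, so the table needs a note saying so.
2. Keep the formula, rename the quantity percent change from baseline with negative values meaning improvement, and reword the sentence to match. This keeps both summaries in the same direction but renames a protocol-specified endpoint, so Sections 5.2 and 7.7.2 must follow and the change must be recorded in Section 11.

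The first option stays closer to the protocol; otherwise the choice is largely one of preference. Either way, apply the same convention in the table shell, the listing and the program. The cost is one formula or one label plus a sign note. Data collection and trial conduct are unaffected.
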